The objective of the proposed research is to adapt and evaluate a peer based dyadic social support health coaching PA intervention to increase PA in SAI women. Social support, self-efficacy and behavioral skills are recognized correlates of PA across racially, ethnically, and socioeconomically diverse populations⁷⁴⁻⁷⁸ and motivational interviewing can enhance lifestyle behavioral change^{79,80}. Nonetheless, research is needed to better understand the most effective approaches for delivering social support interventions to increase PA in SAI women. The proposed research is able to leverage the knowledge and infrastructure from two ongoing studies of this research team, one involving qualitative focus groups with SAI women regarding barriers and facilitators to PA including the role of social support, and a large R01 efficacy trial testing a peer based dyadic social support health coaching PA intervention in inactive Hispanic and African American women.

Hypothesis: We hypothesize that this innovative culturally adapted, social support-based intervention will be feasible and acceptable among sedentary population of SAI women in the U.S.

Specific Aims: This project is built on evidence that peer-based social support, motivational interviewing, and mobile technologies can be utilized to strengthen self-efficacy and social supports to promote increased PA in minority women. This study is able to leverage two ongoing studies, one that involves qualitative focus group research specifically with SAI women regarding barriers and facilitators to PA, and a large R01(**R01HL155310**) efficacy trial testing a dyadic health coaching intervention in inactive Hispanic and African American women.

Aims are: 1) Assess the feasibility of recruitment, retention outcomes, intervention engagement (i.e., number of counseling sessions completed, use of Fitbit, review of newsletters), and completion of study procedures in a preliminary group of a social network-based 12-week dyadic behavioral PA intervention in sedentary SAI women. 2) Explore preliminary effects of receiving the intervention on intermediate outcomes: self-reported and objective moderate-to-vigorous physical activity (MVPA), social support, and self-efficacy at 12 weeks.

OBJECTIVES	OUTCOME MEASURES (a.k.a. ENDPOINTS), with TIMEPOINTS for each
------------	--

Primary	

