The proposed single-arm pilot study will test the feasibility of recruitment, retention, acceptability and implementation of study procedures of a 12-week dyadic behavioral intervention to promote positive and sustained change in MVPA, social support, and self-efficacy among inactive SAI women in Houston, TX. The intervention will target 10 dyads of inactive SAI women and will include dyad-based Zoom coaching delivered by a certified holistic nurse coach using a motivational interviewing approach to promote social support between dyad members as they practice how to be supportive partners; employing a Fitbit device to monitor one's own and one's exercise partner's PA; and dissemination of PA-related health education.

Study Population and Eligibility

For this study, participants will be SAI women aged 40-65 years living in Houston, Texas; insufficiently active (PA<150 minutes/week); physically able to engage in moderate PA; speak and read English; able to enroll with an eligible adult female partner who does not live in the same household; willing to use the Fitbit app/device; own a smartphone that is compatible with Fitbit software (up to 223.3 MB on iPhone or 165 MB on Android) 9); able and willing to send and receive text messages; and Blood pressure reading <160/100 mm Hg, or with medical clearance. Exclusion criteria include SAI women with a current/planned pregnancy; cannot speak and read English, those participating in a PA or weight loss program, and those diagnosed with a physical disability that interferes with their ability to be physically active.

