This study encourages increased participation in physical activity of a moderate nature. This activity may result in mild physical discomfort (e.g., sore muscles, stiffness) for some participants. These effects have no long-term negative health implications and are a normal consequence of activity. However, more serious potential risks include pulled muscles, heart problems, chest tightness or discomfort, shortness of breath, and accidental injuries, such as falling. Possible outcomes could include referral to the participant's primary care physician and/or other physician. Our inclusion/exclusion criteria were designed to exclude participants who should not participate in regular light-to-moderate physical activity based on their responses to the PAR-Q and blood pressure measures without the authorization of a healthcare provider.

Study Withdrawal/Discontinuation

Participants may withdraw from this study at any point in time without repercussion, by simply indicating their desire to withdraw to a study team member.

Criteria for Removal from the Study:

- Participant or clinician request
- Inability to contact the patient for 1 month (up to 6 attempts will be made)
- Completion of study
- Study team determined the patient was no longer eligible

- Sessions were not productive
- Deceased
- Health status declined

All data captured from withdrawn participants will be considered evaluable and used for this study, unless a withdrawn participant requests to have their data destroyed.

Data and Safety Monitoring

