The feasibility of the intervention will be determined by comparing the percentages for overall recruitment and retention at week 12 to their target values of 80% and 70%, respectively. A secondary feasibility assessment will determine the proportion of intervention participants who take part in each of the intervention components (i.e., number of counseling calls completed, use of Fitbit, receipt and review of newsletters). In addition, every attempt will be made to query subjects lost to follow-up to ascertain the reason for drop out or barriers to participation. Feasibility will be measured by calculating the rates of enrollment, retention, assessment completion, and treatment adherence. The enrollment rate will be the proportion of those meeting inclusion criteria that enrolled, while the retention rate will be the proportion enrolled that complete the study. Assessment completion will be calculated as the proportion of assigned data collection forms that were completed. Treatment adherence will be calculated as the proportion of intervention sessions attended.

To explore trends in the outcomes data, means and standard deviations will be calculated for the instrument scores at baseline and week 12. As hypothesis testing is not the objective of a pilot

study¹¹⁸, these descriptive statistics will only be used to inform effect size estimation. Since the effect sizes in a pilot study may overestimate or underestimate the true effect sizes¹²⁰ the obtained effect size estimates will be considered in combination with clinically significant effect sizes for the outcome variables in determining the sample size for a future trial.

Power Analysis: The primary aims do not require power calculations given the focus on feasibility study.

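### The Aim 2 effect size rests on separate baseline and week-12 means that need not cover the same women; compute it from within-woman change and show the non-completers' baseline

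*Combined protocol and SAP*

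**What the plan says.** Under Specific Aims, Aim 2 is to "Explore preliminary effects of receiving the intervention on intermediate outcomes", namely self-reported and objective activity, social support and self-efficacy at 12 weeks. The Statistics section plans one analysis for these outcomes: "means and standard deviations will be calculated for the instrument scores at baseline and week 12". It adds that "these descriptive statistics will only be used to inform effect size estimation". The estimates are then weighed together with effect sizes judged clinically significant when a future trial is sized, and the section warns that pilot effect sizes can err in either direction.

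Four other statements determine who can be in each mean:

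- Study Design: "The intervention will target 10 dyads of inactive SAI women", that is 20 women in a single arm.
- Study Withdrawal/Discontinuation: "All data captured from withdrawn participants will be considered evaluable and used for this study", unless a woman asks for her data to be destroyed.
- Data Collection and Study Procedures: assessments take place at baseline and immediately after the intervention, about three months later, and at no other time.
- Statistics: feasibility is judged by "comparing the percentages for overall recruitment and retention at week 12 to their target values of 80% and 70%, respectively", and "the retention rate will be the proportion enrolled that complete the study". Women lost to follow-up are asked for their reasons; no outcome assessment of them is described.

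The plan states no analysis set, no within-woman change and no rule for missing week-12 scores.

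**The concern.** Followed as written, the plan puts a woman who leaves early into the baseline mean and not into the week-12 mean. The difference between the two means then mixes two things: how much the remaining women changed, and how the remaining women differed at the start from those who left. The second part is not change at all.

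A further issue remains even when the same women are in both means. A change measured only in women who stayed describes those women, and it differs from the change over everyone enrolled if leavers responded differently. The withdrawal section makes outcome-related loss plausible, because its removal reasons include unproductive sessions and a decline in health.

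What is at stake is the Aim 2 number that the study hands to the next trial. As planned, a reader of the results could neither see nor bound how much of it comes from who was left.

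**Working it through.** **Inputs from the documents.** 10 dyads, so 20 women (Study Design). Retention target 70% at week 12 (Statistics), so 0.70 × 20 = 14 retained and 6 lost if the target is only just met. The plan gives no effect size, SD, alpha or power, so it has no figure to reproduce.

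**Assumptions, for illustration only.** Outcome SD = 1; baseline gaps of ±0.5 SD; a completers' gain of 0.50 SD; non-completers' gain of zero, half or all of that.

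**Step 1: what the difference of the two means contains.** Let r be retention, and let C and D be the baseline means of completers and non-completers. The baseline mean over all women is rC + (1 − r)D. Then

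week-12 mean (completers) − baseline mean (all) = completers' mean change + C − [rC + (1 − r)D] = completers' mean change + (1 − r)(C − D).

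This is exact. At r = 0.70 and C − D = +0.5 SD, the added term is 0.30 × 0.5 = +0.15 SD. At C − D = −0.5 SD it is −0.15 SD. At C = D it is zero.

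**Step 2: completers' change against all-enrolled change.** If non-completers gain a fraction f of the completers' gain g, the all-enrolled change is g[r + (1 − r)f]. With g = 0.50 and r = 0.70:

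- f = 0: 0.50 × 0.70 = 0.35 SD.
- f = 0.5: 0.50 × 0.85 = 0.425 SD.
- f = 1: 0.50 SD, no discrepancy.

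**Step 3: the two parts together (g = 0.50, r = 0.70).**

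| C − D | f | Difference of the two means | All-enrolled change |
|---|---|---|---|
| 0 | 0 | 0.50 | 0.35 |
| +0.5 | 0 | 0.65 | 0.35 |
| −0.5 | 0 | 0.35 | 0.35 |
| −0.5 | 1 | 0.35 | 0.50 |
| 0 | 1 | 0.50 | 0.50 |

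The planned contrast can be too high, too low or correct. Restricting both means to completers returns 0.50 in every row. That removes the baseline shift but does not recover 0.35 where leavers gain nothing.

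**Step 4: dependence on retention.** With a 0.5 SD gap, the shift is 0.15, 0.10 and 0.05 SD at 70%, 80% and 90% retention. With f = 0 and g = 0.50, the all-enrolled change is 0.35, 0.40 and 0.45 SD. Both discrepancies vanish at full retention.

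**Step 5: what it could mean for sizing, as illustration.** Take a two-arm comparison, two-sided 5%, 80% power and normal approximation: n per arm = 2(1.96 + 0.842)²/d² = 15.70/d². For d = 0.50 this is 62.8, so 63. For d = 0.35 it is 128.2, so 129. In the opposite case, where the contrast shows 0.35 and the truth is 0.50, the error runs the other way: 129 planned where 63 would do.

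**Step 6: sampling error for comparison.** Treat women as independent and assume a correlation of 0.6 between visits. The variance of the planned contrast is 1/14 + 1/20 − 2(0.6)/20 = 0.0614, so its standard error is about 0.25 SD.

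**The case against.** Several points on the other side stand.

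- **The plan writes no effect-size formula.** It does not say that the effect size is the completers' week-12 mean minus everyone's baseline mean, nor in which summary withdrawn women's data are used. The mismatch is the direct reading of the Statistics and withdrawal sections together, not an explicit statement.
- **The direction is open.** A reader might infer that the estimate must be inflated. Nothing in the documents says where leavers start or how they respond, and Step 3 shows that the error can be zero or reverse.
- **The next trial is not sized on this number alone.** A reader might infer that it will be underpowered. The plan weighs the estimate beside clinically significant effect sizes, and the figures in Step 5 rest on assumed gains and on treating a single-arm change as a between-arm difference.
- **Aim 2's wording may fit completers.** Women who left did not receive the whole intervention, so a completers' summary is a defensible target, and without a control arm no version isolates an intervention effect. But if completers are the target, the planned contrast still misses it by the term in Step 1.
- **Fitbit data are collected during the intervention.** For objective activity, information captured before withdrawal may exist, so the mismatch is firmest for the visit-based instruments.
- **Scale.** The 70% is a target, not a forecast, and a standard error near 0.25 SD exceeds the 0.15 SD illustrated. That limits the practical weight of the point. It is not a reason to keep a shift that can be removed without recruiting anyone.

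The plan's general warning about pilot effect sizes softens the consequence. It does not say who is in each mean or let a reader see the shift.

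**Conclusion.** The point holds as a mismatch of analysis sets. Up to 20 women can contribute to the baseline mean and as few as 14 to the week-12 mean at the retention target, and their difference carries an extra term of (1 − retention) × baseline gap. That algebra is exact; its size here is not known. At 70% retention, an assumed gap of 0.5 SD moves the result by 0.15 SD in either direction, and the term is zero if dropout is unrelated to baseline. Separately, an assumed completers' gain of 0.50 SD with no gain in leavers is 0.35 SD over all enrolled, which would correspond to 129 rather than 63 per arm. Those sample sizes are illustrative.

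The documents do not support going further, to a known upward bias or to a prediction that the next trial will be undersized. The removal reasons make outcome-related loss plausible, no more. The change is still worth making: it is a better summary of the same data, at almost no cost.

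**What to change.** In the Statistics section, state for each Aim 2 outcome that:

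1. The effect size is computed from within-woman change (mean and SD) in women with both assessments, with the number of women given.
2. The baseline mean of women without week-12 data is shown beside that of completers.
3. One all-enrolled sensitivity value is added, for example with no change for women without week-12 data. Label it as an assumption and not as a lower bound, since some of these women could have worsened. Where Fitbit data were captured before withdrawal, use them rather than replacing them.
4. Both values are considered, with the clinically significant effect sizes, when the next trial is sized.

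The cost is a few sentences and a few extra table columns, with no new visits or data. The downside is that the reported effect may be smaller, and the sensitivity value brings an assumption that must be stated.
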